## 4. SELECTION AND WITHDRAWAL OF SUBJECTS

Male and female subjects, 18 years of age or older, with a clinical diagnosis of stable AA, AU or AT of the scalp, who meet all the inclusion criteria and none of the exclusion criteria, will be eligible to enroll in this study.

### 4.1. Subject Inclusion Criteria

Subjects must meet the following criteria to be eligible for participation in the study:

1. Able to comprehend and willing to sign an Informed Consent Form (ICF).
2. Male or non-pregnant, non-nursing female  $\geq$  18 years old at the time of informed consent.
3. Have a clinical diagnosis of stable AA, AU or AT (Stable is defined as no current areas of spontaneous terminal scalp hair regrowth).
4. Have a Severity of Alopecia Tool (SALT) score of at least 30% to 100% total scalp hair loss determined by the study investigator at Screening (Visit 1) and Baseline (Visit 2).
5. Subjects with 30% to 95% scalp hair loss (based on SALT score) must have an assessment of “no hair” or “a little hair” in the target scalp patch based on both the Clinician and Subject Alopecia Scalp Appearance Assessment (ASAA). The target patch is defined as the most bothersome patchy area of hair loss as identified by the subject (Refer to Section 7.1).
6. Have a duration of the current episode of stable scalp hair loss for a minimum of 6 months and a maximum duration of hair loss of 12 years (inclusive). [Current episode is defined as the period of the current presentation of hair loss (AA, AU or AT)].
7. If the subject is a woman of childbearing potential (WOCBP), she must have:
  - Negative serum pregnancy tests at Screening (Visit 1); and
  - A negative urine pregnancy test at Baseline (Visit 2); and
  - Agree to not be planning a pregnancy during the study duration and use a highly effective method of contraception during the study and for 30 days after the last dose of study medication. (Refer to Section 8.4.2).
8. Be in good general health and free of any known disease state or physical condition which, in the investigator’s opinion, might impair evaluation of the subject or which might expose the subject to an unacceptable risk by study participation.
9. Be willing to maintain the same hair style and hair dyeing throughout the study period. Subjects who shave their scalp must be willing to refrain from shaving their scalp for at least two weeks prior to each study visit, as determined by the investigator based on the ability to assess visible scalp hair growth. Hair trimming outside the treatment areas to maintain the current hair style is permitted.
10. Be willing and able to follow all study instructions and to attend all study visits.
11. Subjects taking hormonal replacement therapies must be on stable doses for 6 months prior to enrollment and remain on a maintenance dose throughout the study.
12. Subjects taking thyroid replacement medication must be on stable doses for 6 months prior to enrollment and remain on a maintenance dose throughout the study.

13. Sexually active male subjects must agree to use a barrier method of contraception with any WOCBP partner(s) from the first dose of study medication to at least 30 days after the last dose of study medication.

## 4.2. Subject Exclusion Criteria

Subjects are excluded from this study if any 1 or more of the following criteria is met:

1. Females who are nursing, pregnant, or planning to become pregnant for the duration of the study and up to 30 days after the last dose of study medication.
2. Diffuse alopecia areata. [Diffuse alopecia areata is defined as the absence of the typical patchy distribution of hair loss (in subjects with  $\leq 95\%$  total scalp hair loss) with hair thinning distributed throughout the scalp.]
3. Concomitant hair loss disorder (by history or physical exam) such as androgenetic alopecia (AGA) or scarring alopecia (*e.g.*, cicatricial alopecia, frontal fibrosing alopecia, etc.). Subjects without a prior known history of AGA or other patterned hair loss disorder who exhibit AGA or other patterned hair loss with regrowth during the study will be allowed to continue in the study.
4. Active skin disease on the scalp (such as psoriasis or seborrheic dermatitis) or a history of skin disease on the scalp that in the opinion of the investigator would interfere with study assessments of efficacy or safety.
5. Active scalp trauma or other condition affecting the scalp that, in the investigator's opinion, may affect the course of AA, AU or AT or interfere with the study conduct or evaluations.
6. The presence of a permanent or difficult to remove hairpiece or wig that will, in the opinion of the investigator, interfere with study assessments if not removed at each visit.
7. History of, or current, severe, progressive or uncontrolled autoimmune, metabolic, hepatic, endocrine, renal, gastrointestinal, pulmonary, cardiovascular, genitourinary, or hematological disease, neurologic or cerebral disorders, or coagulation disorders that, as determined by the Investigator, would preclude participation in and completion of study assessments.
8. History of, current or suspected systemic or cutaneous malignancy and /or lymphoproliferative disease, other than subjects with a history of adequately treated and well healed and completely cleared non-melanoma skin cancers (*e.g.* basal or squamous cell carcinoma) treated successfully at least 1 year prior to study entry with no evidence of disease.
9. Evidence of active or latent bacterial (including tuberculosis) or viral infections at the time of enrollment, or history of incompletely treated or untreated tuberculosis. Subjects who have completed therapy for latent tuberculosis may participate. Refer to Exclusion Criterion 12 for herpes zoster, herpes simplex, or cytomegalovirus infections.
10. History of serious local infection (*e.g.*, cellulitis, abscess) or systemic infection including but not limited to a history of treated infection (*e.g.*, pneumonia, septicemia) within 3 months prior to Baseline. Subjects on an antibiotic for a nonserious, acute local infection must complete the course prior to enrollment into the study.
11. Positive for HIV, Hepatitis B or C. Subjects with serologic evidence of Hepatitis B vaccination (HepB surface Ab without the presence of Hep B surface Ag) will be allowed to participate.

12. History of recurrent herpes zoster (more than one episode) or disseminated herpes zoster (a single episode) or disseminated herpes simplex (single episode) or cytomegalovirus (CMV) that resolved less than 2 months before study enrollment. Subjects with a history of frequent outbreaks of Herpes Simplex Virus (defined as 4 or more outbreaks a year).
13. Clinically significant laboratory abnormalities at screening that, in the opinion of the Investigator, would make the subject a poor candidate for the study. [Subjects with any Screening laboratory values meeting the Study Medication Interruption Criteria found in [Table 2](#) must have repeat lab testing performed with results meeting the minimum criteria for resumption in order to initiate treatment at Baseline (Visit 2)].
14. Subjects with absolute neutrophil count  $<1,800/\mu\text{L}$ , or platelet count  $<130,000/\mu\text{L}$ .
15. Subjects who have received any of the following treatments for the timeframes specified below:
  - Disease Modifying Anti-Rheumatic Drugs (DMARDs), Biologics or immunosuppressants, including but not limited to: anakinra, adalimumab, azathioprine, corticosteroids, cyclosporine, etanercept, infliximab, methotrexate, TNF inhibitors, ustekinumab within 1 month or 5 half-lives (whichever is greater) of Baseline (Visit 2).
  - Plaquenil within 2 months of Baseline (Visit 2).
  - JAK inhibitors (oral or topical) within 6 months of Baseline (Visit 2).
  - Intralesional steroids or platelet rich plasma injections in the scalp within 1 month of Baseline (Visit 2).
  - Topical treatments on the scalp with anthralin, bimatoprost, corticosteroids, diphencyprone, diphenylcyclopropanone (DPCP), squaric acid dibutylester (SADBE), minoxidil, pimecrolimus, or tacrolimus within 1 month of Baseline (Visit 2).
  - Phototherapy (narrow band Ultraviolet B [NB UVB] or broadband therapy) within 4 weeks of Baseline (Visit 2).
16. Participation in an investigational drug or device trial in which administration of an investigational drug or device occurred within 30 days or 5 half-lives (whichever is longer) of Baseline (Visit 2).
17. Any condition possibly affecting oral drug absorption, e.g., gastrectomy, clinically significant diabetic gastroenteropathy, or certain types of bariatric surgery such as gastric bypass. Procedures such as gastric banding are not exclusionary.
18. Sensitivity to any of the ingredients in the study medications.
19. Unwillingness to refrain from weaves, hair extensions, or shaving of the scalp for at least two weeks prior to a study visit, at the discretion of the investigator, based on the ability to assess hair growth.
20. Screening ECG findings of:
  - QTcF  $>450\text{msec}$  for males or  $>470\text{msec}$  for females (use of the ECG algorithm is acceptable for this purpose)
  - Heart rate  $\leq 45$  or  $\geq 100$  beats/minutes (A subject with a heart rate  $\leq 45$  beats/min may be enrolled if in the opinion of the investigator the heart rate is not clinically significant).
  - Rhythm disturbance other than sinus arrhythmia or ectopic supraventricular rhythm (ectopic atrial rhythm)

- Conduction disturbance including PR >240msec, pre-excitation (delta wave and PR <120msec), second degree or higher AV block
  - Acute or chronic signs of ischemia
  - Left Bundle Branch Block
  - Prior myocardial infarction
21. Vaccination with a live or attenuated vaccine within 6 weeks prior to Baseline (Visit 2) or planned vaccinated with these vaccines at any time during treatment or within 6 weeks following discontinuation of study medication.
  22. Participation in an investigational study with ATI-502 Topical Solution.
  23. Subjects unwilling to have photographs taken for study purposes.

### **4.3. Subject Withdrawal Criteria**

Subjects will be informed that they are free to withdraw from the study at any time and for any reason. The investigator may remove a subject from the study if, in the investigator's opinion, it is not in the best interest of the subject to continue the study. Examples of other reasons subjects may be discontinued from the study are: a change in compliance with an inclusion or exclusion criterion, occurrence of AEs, occurrence of pregnancy, use of a prohibited therapy or subject is unwilling or refuses to continue with the protocol defined study visits and/or subject withdraws consent (Refer to Section 3.5 for study medication discontinuation or termination criteria).

In case of premature discontinuation from study participation, all efforts will be made to perform all Week 24 (Visit 9) assessments. The date the subject is withdrawn from the study and the reason for discontinuation must be recorded in the subject's electronic case report forms (eCRFs). All withdrawn subjects with ongoing AEs will be followed until the event has resolved or stabilized, until the subject is referred to the care of a local health care professional, or until a determination of a cause unrelated to the study medication or study procedures is made.

## 5. TREATMENT OF SUBJECTS

### 5.1. Study Medication Administration

Study medication will be self-administered by the subject. Study staff should instruct the subject not to take study medication on an empty stomach. Subjects will be instructed to take one single-dose bottle of study medication followed by a full glass of water, within approximately 30 minutes after the morning meal and after approximately 8 to 12 hours, to take the second dose within approximately 30 minutes after the evening meal as detailed in study medication instructions in [Appendix 15](#). Subjects should not mix/dilute the medication in other liquids, rather they should take the study medication as indicated in the directions provided.

The investigational site staff will dispense a sufficient supply of study medication at the visits detailed in the Schedule of Assessments (Table 3) and will review the study medication instructions as detailed in [Appendix 15](#). The investigational site staff dispensing and reconciling the study medication should not be involved in the investigator or subject efficacy assessments. Subjects will be given a compliance record to complete. At each study visit, subjects should bring the study medication including used and unused bottles and the completed compliance record. The study staff will review the compliance record, used and unused bottles and the study medication instructions.

### 5.2. Concomitant Medications

Concomitant therapies are any new or existing therapies received from Screening (Visit 1) until discharge from the study. Concomitant therapies include drug (e.g. prescription and over the counter [OTC]), and non-drug (e.g., chiropractic, physical therapy, energy-based treatments).

Subjects will be allowed to take medications not restricted by the protocol as long as they have been reviewed by the investigator and will not affect efficacy or safety. Vitamins, minerals, and dietary supplements are permitted while on study if the subject has been on a stable dose prior to study entry and, in the opinion of the Investigator, will not affect the safety or efficacy of the subject during the study. Topical hair and scalp products (shampoos, conditioners, styling products) should be reviewed by the Investigator and are permitted if, in the Investigator's opinion, they will not affect the safety or efficacy of the subject during the study. Use of hair dyes is permitted during the study if the subject uses the same hair dye throughout the study. If in the opinion of the Investigator, the hair dye interferes with study assessments the subject may be directed to wait until after the study visit to dye his or her hair. Efforts should be made to keep the hair care regimen the same throughout the duration of the study.

Topical therapies such as topical corticosteroids are permitted if they are not applied on or near the scalp and are not used for hair growth in other areas. Inhaled or intranasal corticosteroids are allowed in the study.

Prior permitted concomitant medications taken within 30 days of beginning treatment with ATI-501 Oral Suspension will be documented in the subject's source document and eCRF. In addition, any new permitted medications administered during protocol treatment and through Week 28 (Visit 10) will be documented in the subject's source document and eCRF.

### 5.3. Grooming

Routine shaving of beard or body hair is allowed during the study as long as the subject refrains from shaving for a period sufficient to show hair growth prior to Visits 6, 9, and 10. Shaving of the scalp must conform to the requirements specified in Inclusion Criterion #9. Subjects are allowed to grow their hair longer than the length at baseline visit, as long as the investigator can assess hair loss and regrowth during the study and hair regrowth is pinned out of the way to show the areas with hair loss at baseline for photographs.

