Week		0	2	4	8	12	16	20	24	28
Treatment Day	-30 to 0	1	15	29	57	85	113	141	169	197
Treatment Window(days)	N/A	N/A	± 3	± 3	± 3	± 3	± 3	± 3	± 3	± 3
SALT Score (prior to ALODEX) 	X	X	X	X	X	X	X	X	X	X
ALODEX Score (after SALT) 	X	X	X	X	X	X	X	X	X	X
Vellus and Indeterminate Hair Assessment	X	X	X	X	X	X	X	X	X	X
Photography (complete scalp)		X		X	X	X	X	X	X	
Subject randomization		X								
Subject instructions 		X		X	X	X	X	X	X	
Dispense study medication 		X	X 	X	X	X	X	X		
Collect study medication and assess compliance 		X	X	X	X	X	X	X	X	X
Concomitant therapies		X	X	X	X	X	X	X	X	X
Adverse events		X	X	X	X	X	X	X	X	X
Abbreviations: CR= Clinician Rating; ET= Early termination Visit; SR= Subject Rating										
 Efficacy assessments completed at Visit 3 are to test the reliability of the clinician and patient reported outcome tools.										
 A written, signed ICF must be obtained from each subject prior to performing any study related procedure ( i.e. , prior to performing vital signs, standardized photography, biopsies, clinical laboratory sampling or urine pregnancy tests).										
 A physical exam includes: general appearance, examination of head, eyes, ears, nose and throat, respiratory, cardiovascular, abdominal, neurological, musculoskeletal, extremities, lymphatic and skin assessment (other than AA).										
 Vitals signs include: oral or ear temperature, blood pressure, heart rate, respiration rate (height and weight at Screening only).										
 Clinical laboratory non-fasting sampling includes: CBC, Chemistry with lipids, Urinalysis. Quantiferon Gold, HIV, Hepatitis B and C, TIBC, Serum Iron, Serum Ferritin, T3, free T4, TSH and Serum Pregnancy should be done at screening visit only.										
 At Select sites: A single 4.5 mL sodium citrate vacutainer should be drawn at Visit 2 (predose) and Visits 4, 6, and 9, 12 hours (± 30 minutes) after the prior evening dose. Subjects participating in the PK analysis should be called the day prior to Visit 4, 6, and 9 to remind them to take their evening dose approximately 11 hours prior to the visit time and to document the time of the evening dose.										

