**7.3.1.2. Alopecia Scalp Appearance Assessment (ASAA) for AT and AU: Clinician Rating (CR) (ASAA-AT/AU: CR)**

**Instructions:** Please mark an “X” in the box (☐) that best describes the appearance of the subject’s **whole scalp** right now. Please select the one response that best represents your answer.

- Full hair, whole scalp completely covered with hair
- Most hair, whole scalp mostly covered with hair
- Some hair, whole scalp somewhat covered with hair
- A little hair, whole scalp mostly exposed
- No hair, whole scalp completely exposed

**7.3.2. Alopecia Facial Hair Appearance Assessment (AFHA) for AA, AT and AU:  
Clinician Rating (CR) (AFHA: CR)**

For subjects with AA, AU or AT, the appearance of the subject's facial hair (eyebrows, eyelashes and if male, beard) will be assessed using the AFHA: CR by the investigator at Baseline (Visit 2) and the visits listed in the Schedule of Assessments ([Table 3](#)).

The AFHA: CR is the investigator's assessment of the subject's facial hair (eyebrow(s), eyelashes, and if male, beard) at a particular point in time. The investigator should NOT refer to any other assessments to assist with these assessments. The investigator or designee will assess the affected facial hair areas (eyebrows, eyelashes and if male, beard) using the scales below and report the one response that best describes the amount of eyebrow, eyelash and if applicable beard hair present. Right and left eyebrow and eyelashes should be evaluated separately. The AFHA is a tool to assess the presence of hair in expected areas of growth. As such, unexpected hair growth (e.g. facial/beard hair in women) should be documented as an adverse event rather than on the AFHA.

**Instructions for item 1a:** Please mark an "X" in the box () that best describes the appearance of the subject's **left** eyebrow hair right now. Please select the one response that best represents your answer.

- Full eyebrow hair
- Most eyebrow hair
- Some eyebrow hair
- A little eyebrow hair
- No eyebrow hair

**Instructions for item 1b:** Please mark an "X" in the box () that best describes the appearance of the subject's **right** eyebrow hair right now. Please select the one response that best represents your answer.

- Full eyebrow hair
- Most eyebrow hair
- Some eyebrow hair
- A little eyebrow hair
- No eyebrow hair

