**Instructions for item 2a:** Please mark an “X” in the box (☐) that best describes the appearance of the subject’s **left** eyelashes right now. Please select the one response that best represents your answer.

- Full eyelashes
- Most eyelashes
- Some eyelashes
- A little eyelashes
- No eyelashes

**Instructions for item 2b:** Please mark an “X” in the box (☐) that best describes the appearance of the subject’s **right** eyelashes right now. Please select the one response that best represents your answer.

- Full eyelashes
- Most eyelashes
- Some eyelashes
- A little eyelashes
- No eyelashes

**Instructions for item 3:** Please mark an “X” in the box (☐) that best describes the appearance of the subject’s beard hair right now. Beard hair can include hair on the chin, cheeks, neck, and above the upper lip. Please select the one response that best represents your answer.

- Full beard hair
- Most beard hair
- Some beard hair
- A little beard hair
- No beard hair

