### 7.3.3. Non-Scalp Hair Loss Assessment (NSHA)

The investigator will assess body hair (axillary, truncal, genital, extremities) and facial hair including nasal hair using a 3-point scale; no hair loss, some hair loss and total hair loss. Nasal hair will be assessed by presence or absence only. These assessments will be completed at Baseline (Visit 2) and the visits listed in the Schedule of Assessments (Table 3) (Olsen, 2011).

**Instructions:** Please mark an “X” in the box () that best describes the appearance of the subject’s body hair loss right now. Please select the one response that best represents your answer.

Mark “X”	Body Hair Loss (axillary, truncal, genital, extremities)	
	B0	No body hair loss
	B1	Some hair loss
	B2	Total body hair loss

**Instructions:** Please mark an “X” in the box () that best describes the appearance of the subject’s nasal hair loss right now. Please select the one response that best represents your answer.

Mark “X”	Nasal Hair Loss	
	NH0	No nasal hair loss
	NH1	Some to total nasal hair loss

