### AFHA

38. Table 14.2.6.1.1 Analysis of Change from Baseline in Alopecia Facial Hair Appearance Assessment (AFHA-ClinRO), Left Eyebrow, ITT Population
39. Table 14.2.6.1.2 Analysis of Change from Baseline in Alopecia Facial Hair Appearance Assessment (AFHA-ClinRO), Right Eyebrow, ITT Population
40. Table 14.2.6.1.3 Analysis of Change from Baseline in Alopecia Facial Hair Appearance Assessment (AFHA-ClinRO), Left Eyelash, ITT Population
41. Table 14.2.6.1.4 Analysis of Change from Baseline in Alopecia Facial Hair Appearance Assessment (AFHA-ClinRO), Right Eyelash, ITT Population
42. Table 14.2.6.1.5 Analysis of Change from Baseline in Alopecia Facial Hair Appearance Assessment (AFHA-ClinRO), Beard, Male Subjects, ITT Population
43. Table 14.2.6.2.1 Analysis of Change from Baseline in Alopecia Facial Hair Appearance Assessment (AFHA-PRO), Left Eyebrow, ITT Population
44. Table 14.2.6.2.2 Analysis of Change from Baseline in Alopecia Facial Hair Appearance Assessment (AFHA- PRO), Right Eyebrow, ITT Population
45. Table 14.2.6.2.3 Analysis of Change from Baseline in Alopecia Facial Hair Appearance Assessment (AFHA- PRO), Left Eyelash, ITT Population
46. Table 14.2.6.2.4 Analysis of Change from Baseline in Alopecia Facial Hair Appearance Assessment (AFHA- PRO), Right Eyelash, ITT Population
47. Table 14.2.6.2.5 Analysis of Change from Baseline in Alopecia Facial Hair Appearance Assessment (AFHA- PRO), Beard, Male Subjects, ITT Population

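### The beard and body-hair no-shaving rule omits Baseline and Visit 3, so beard change from baseline can show improvement that is only regrown shaving

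*Protocol*

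**What the plan says.** Protocol 5.3 (Grooming) permits routine shaving of beard or body hair as long as the subject "refrains from shaving for a period sufficient to show hair growth prior to Visits 6, 9, and 10". No other visit is named.

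Protocol 7.3.2 says that facial hair, including the beard in men, "will be assessed using the AFHA: CR by the investigator at Baseline (Visit 2) and the visits listed in the Schedule of Assessments"; 7.2.2 (subject-rated AFHA) and 7.3.3 (NSHA) follow the same schedule. The schedule in SAP 1.2 marks AFHA (subject and clinician) and NSHA at Visits 2, 3, 6, 9 and 10. Neither is rated at Screening.

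The beard item asks about appearance at the moment of rating, on five levels from full to none, and adds that "Beard hair can include hair on the chin, cheeks, neck, and above the upper lip". It has no response for a shaved beard; the only not-applicable option, on the subject form, is for women.

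The one shaving rule that covers every visit is Inclusion Criterion 9: "Subjects who shave their scalp must be willing to refrain from shaving their scalp for at least two weeks prior to each study visit". It concerns the scalp, as does Exclusion Criterion 19.

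Footnote 1 to Protocol Table 3 gives the purpose of the Visit 3 ratings: "Efficacy assessments completed at Visit 3 are to test the reliability of the clinician and patient reported outcome tools".

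SAP Section 9 lists a dedicated beard table, "Analysis of Change from Baseline in Alopecia Facial Hair Appearance Assessment (AFHA-ClinRO), Beard, Male Subjects, ITT Population" (Table 14.2.6.1.5), a subject-rated counterpart (14.2.6.2.5), and a body-hair shift table from Baseline to Week 24 (14.2.14). SAP 6.2.5 compares AFHA change in each active arm with placebo by a Wilcoxon rank sum test at each visit.

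**The concern.** By requiring visible growth before Visits 6, 9 and 10, Section 5.3 accepts that shaving spoils these ratings. It then leaves uncontrolled the visit from which every change is measured. A site that follows the rule exactly may rate a shaved face at Baseline and an unshaved one at Week 24, so the error runs in one direction, towards improvement.

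Three uses of the data are exposed:

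- within-arm beard change from baseline, clinician- and subject-rated;
- the body-hair shift table;
- any Visit 2 to Visit 3 agreement calculated for the beard item, where disagreement could come from shaving rather than from the tool.

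The Week 2 beard comparison is weak for a related reason: shaving is uncontrolled at both of its visits, so spurious change can go either way.

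**Working it through.** The plan gives no figure for this point, so there is none to reproduce. The check sets the rule against the schedule, then illustrates direction and size on stated assumptions.

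**Rule against schedule**

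| Visit | AFHA and NSHA rated (SAP 1.2) | Beard/body shaving rule (Protocol 5.3) | Scalp shaving rule (Inclusion 9) |
|---|---|---|---|
| 2 (Baseline) | yes | no | yes |
| 3 | yes | no | yes |
| 6 | yes | yes | yes |
| 9 (Week 24) | yes | yes | yes |
| 10 | yes | yes | yes |

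The rule names every rating visit after Visit 3 and omits the first two. SAP 4.3.6 takes as baseline the last non-missing value before study medication. As AFHA and NSHA are not scheduled at Screening, that value is the Visit 2 rating.

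**Illustration (assumptions, not document figures)**

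Score the beard 1 (full) to 5 (none); under SAP 6.2.5 a falling score is improvement. Let *t* be the rating a man would get unshaved, uniform on 1 to 5 (mean 3, variance 2), with no true change and no rater error. A fraction *s* of men are shaved and rated 5, independently at Visits 2 and 3. All are unshaved at Week 24.

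- Chance of false improvement of at least 1 point: *s* × 4/5, since a man whose true rating is already 5 cannot move.
- Mean false change: 3 − (3 + 2*s*) = −2*s*.
- Visit 2/3 intraclass correlation: covariance 2(1 − *s*)² over variance 2(1 − *s*)(1 + 2*s*), which is (1 − *s*)/(1 + 2*s*).

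| *s* | False improvement ≥1 point | Mean false change | Visit 2/3 ICC |
|---|---|---|---|
| 0 | 0% | 0 | 1.00 |
| 10% | 8% | −0.2 | 0.75 |
| 20% | 16% | −0.4 | 0.57 |
| 30% | 24% | −0.6 | 0.44 |
| 50% | 40% | −1.0 | 0.25 |

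A simulation on the same assumptions gave the same values to rounding.

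**Comparison with placebo**

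With the same *s* in both arms and 10 men per arm (assumed), the simulated false-positive rate of the rank sum test was 0.6% at *s* = 10% and 3.6% at *s* = 50%, so it stayed below 5%.

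**Timing**

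Protocol Version 5.0 is dated 09APR2019, and the synopsis estimates last completion in July 2019. Counting back from 31 July, 24 weeks (168 days) gives 13 February and 28 weeks (196 days) gives 16 January for the last Baseline. Visit 3 follows 14 days later. On those estimates every Visit 2 and Visit 3 preceded this version.

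**The case against.** The best case on the other side is that the gap does little harm.

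- **It does not favour the drug.** A reader might infer that false improvement biases the trial towards ATI-501. The documents do not support that. Allocation is randomised and blinded, so shaving habits should be similar across arms, and AFHA change is tested against placebo. This stands: the comparison gains noise, and the bias is in within-arm change.
- **It does not undo the Visit 3 reliability test.** A reader might infer that it does. Beard is one of five AFHA items and applies to men only; the eyebrow, eyelash, scalp and other questionnaire ratings do not depend on beard shaving. Psychometrics are outside this SAP (Section 1), and the protocol says only that they may include reliability. Whether beard agreement will be calculated cannot be seen.
- **A fixed point shift cannot be claimed.** One could reckon a 4-point swing in one of about 12 men per arm as 4/12 = 0.33 points on the arm mean. That takes the most extreme rating, an assumed half-male split, and a mean, whereas the plan reports frequencies and a rank test.
- **Fewer subjects may be exposed than it seems.** About 45 of 95 are to have AT or AU, and AU means loss of all body hair (Protocol 1.1), so those with AU have little to shave. NSHA asks about hair loss over several body regions, so raters may partly discount shaving, and its table carries no test. This stands, and makes beard the stronger case.
- **Unseen instructions may help.** Protocol 7 promises sites detailed rating instructions, and 7.2.2 has staff educate subjects before each AFHA. This is possible but not shown, and it would not change the visit list in 5.3.

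**Conclusion.** The gap is real, and nothing in the documents closes it. Under Section 5.3 as written, a beard rating at Baseline can be invalid, and within-arm beard change to Week 24 can then show improvement without any treatment effect. The body-hair shift table may be affected to a lesser degree. Any Visit 2 to Visit 3 agreement for the beard item could partly measure shaving.

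The point is minor. It touches one item of one secondary endpoint, in men, and one descriptive table. The size is unknown: the documents give neither the number of men who shave nor the sex mix, and the tabulated values rest on the assumed uniform scores and on every shaved man being placed in the lowest category. That the placebo comparison gains noise rather than bias rests on shaving being similar across arms.

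**What to change.** Change the visit list in Protocol 5.3 to Visits 2, 3, 6, 9 and 10 for any subject still to be rated at those visits. On the estimated dates there may be none, so the following matters more for this trial.

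For subjects already past those visits:

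1. Flag beard or body hair shaved at Baseline or Visit 3 where source notes record it, and report how many have unknown status. No form or schedule item in the documents captures shaving, so the flag will be incomplete.
2. Repeat Tables 14.2.6.1.5, 14.2.6.2.5 and 14.2.14 without subjects flagged at Baseline, as a sensitivity analysis only, because exclusion based on incomplete notes can itself select.
3. Omit subjects flagged at either visit from any Visit 2 to Visit 3 beard reliability estimate.
4. State the limitation wherever within-arm beard change is reported.

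The cost is one protocol phrase, a small source review, and slightly fewer subjects in the sensitivity tables. The primary analysis does not change.
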